#### 4.1.3. Baseline Virtual Visit (Day 1)

After completing the 28-day run-in period, eligible participants will have 3 days to complete baseline activities. Participants will attend a Baseline Visit via a telephone call to review and confirm eligibility. Participants will be considered eligible for study entry based on all of the following criteria:

- Continuing to meet all other inclusion and no exclusion criteria, based on investigator assessment.
- Understanding of and adherence to the onboarding requirements and the Study App
- Reporting within the Study App between 4-14 migraine days (inclusive) during the 28-day run-in period.
- Agreeing to complete the 12-week study intervention in good faith at the time of baseline virtual visit.

Eligible participants will then be randomly assigned in a 1:1 ratio (CT-132:Digital Control). The Study App downloaded during the run-in period will be utilized to deliver the full therapeutic app. Participants will continue to utilize the eDiary component in the Study App throughout the study.

The process for activating and accessing the full therapeutic application during the Baseline Visit will be the same for CT-132 digital intervention and the Digital Control. The randomization process electronically unlocks one of two experiences in the Study App: the CT-132 investigational therapy or the Digital Control. Study staff will complete the randomization process by giving the participant a code to proceed in the Study App. This code serves as a gatekeeper to confirm that the randomization process has been completed correctly and that the participant may continue in the study. This randomization process is designed in a way to minimize unblinding risk for the participant and the study staff. Participants are considered enrolled upon randomization.

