### 7.2. Participant Discontinuation/Withdrawal from the Study

Study staff should make every effort to encourage participants to remain in the study and to continue to use the Study App. A participant may withdraw from the study at any time at their own request or may be withdrawn at any time at the discretion of the investigator for safety, behavioral, or compliance reasons. This is expected to be uncommon.

A participant cannot withdraw consent for use of data already collected as part of the study. If the participant withdraws consent for disclosure of future information, the sponsor may retain and continue to use any data collected before such a withdrawal of consent.

Participants who prematurely discontinue study participation must complete the early termination procedures as described in the SoA (Section 1.2). Participants who discontinue use of the Study App prematurely should ideally be observed until the end of the study as if they were still using the Study App. The Study App on the discontinued participant's smartphone device will be disabled as described in Section 6.2. For all participants, the reason for discontinuation (e.g., AEs) must be recorded in the eCRF. These data will be included in the study database and reported.

Participants who are not actively using the Study App may be less motivated to adhere to the study visit schedule. Investigators and study staff should work to detect early signs of waning interest and encourage continued participation.

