2.2. Primary Estimand

The primary estimand will be the effect of the digital therapeutic (CT-132) on number of MMDs regardless of use of prohibited medications, adherence to treatment or early termination for any reason.

This estimand considers the following intercurrent events:

- Use of prohibited medications
- Lack of adherence
- Early discontinuation due to any reason

Since participants may use their prescribed medication to treat episodic migraine (including changes in medication or dosage) as needed while continuing to use the Study App, and since the study population is defined as participants diagnosed with migraine and taking first- and second-line preventive medications, the use of these medications is not considered an intercurrent event.

Attributes of the primary estimand:

- The **treatment condition** of interest is CT-132 compared to a digital control, both alongside prescribed medications, to treat episodic migraine
- The **population** is late adolescents and adults with episodic migraine who fulfill all of the inclusion criteria and none of the exclusion criteria for the study
- The **endpoint** to be considered is the change from baseline (28-day run-in period) in MMDs to week 12 (previous 28 days, Weeks 9-12)
- The **population-level summary** is the least squares mean (LSM) difference between CT-132 and the digital control

Strategies for Addressing Intercurrent Events in Primary Estimand

- Use of prohibited medications: In case of use of prohibited medications, participants will be discontinued from the study and the Study App will be disabled for them. Data accumulated until the Study App is disabled will be included in the analysis. This approach complies with the treatment policy strategy.
- Lack of adherence: The treatment effect of CT-132 will be estimated regardless of lack of adherence to lessons and activity. This approach complies with the treatment policy strategy.

• Early discontinuation due to any reason: The treatment effect of interest is regardless of early discontinuation of treatment which complies with the treatment policy strategy. For that reason, data that does not exist after early discontinuation will be considered as missing data, and will be imputed as described in Section 6.3.

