8.5.5. Change in the number of headaches with at least moderate severity from baseline (28-day run-in period) to Week 12 (previous 28 days, Week 9 through Week 12)

This endpoint will be performed on the mITT analysis set, in addition to the ITT analysis set.

Each recorded headache's severity will be scored in the following manner:

- None = 0
- Mild = 1
- Moderate = 2
- Severe = 3

Headaches that started at one period and ended in the following period will be assigned to the period in which the headache started.

The change from run-in will be calculated as (Weeks 9-12 number of headaches with at least moderate severity – run-in number of headaches with at least moderate severity).

An ANCOVA model will be used to analyze this endpoint. The dependent variable is the change in number of headaches with at least moderate severity from run-in period to Week 9-12 for each participant.

The model will adjust for the following covariates: treatment arm and number of headaches with at least moderate severity at run-in period

This analysis will use observed data only.

8.5.6. Change from baseline in the Migraine-Specific Quality-of-Life Questionnaire v2.1 (MSQ) total score at Week 12

The MSQ is a 14-item questionnaire that is completed at baseline, Week 4, Week 8, and Week 12. Each item consists of 6 possible responses, scored 1 to 6. Higher scores represent more severe migraines.

For the purpose of calculating the MSQ total score, the responses to the 14 items will be reverescoded (scores 1,2,3,4,5,6 will be converted to 6,5,4,3,2,1 respectively)

For each visit, the MSQ score (after reverse-coding) will be calculated as:

Total score = ([sum of the 14 reversed item scores - 14] / 70) * 100

In case of missing items, the MSQ score for the visit will be considered missing.

An ANCOVA model will be used to analyze this endpoint. The dependent variable is the change from baseline in MSQ to week 12 for each participant.

The model will adjust for the following covariates: treatment arm and baseline MSQ.

This analysis will use observed data only.

8.5.7. Change from baseline in the Migraine-Specific Quality-of-Life Questionnaire v2.1 (MSQ) total score at Week 8

This endpoint will be analyzed in the same manner as described in Section 8.5.6, using the Week 8 assessment.

8.5.8. Change from baseline in the Migraine-Specific Quality-of-Life Questionnaire v2.1 (MSQ) total score at Week 4

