This endpoint will be analyzed in the same manner as described in Section 8.5.6, using the Week 4 assessment.

8.5.9. Change from baseline (28-day run-in period) in the Migraine Disability Assessment (MIDAS) to Week 12

The MIDAS questionnaire assesses the impact the migraine has on the participant's life. It consists of 5 questions regarding the number of days impacted. In addition, there are two questions for physician use. The endpoint will use only the first 5 questions. The MIDAS score for a visit is the sum of responses of the first 5 questions. In case of missing items, the MIDAS score for the visit will be considered missing.

This endpoint will be analyzed using Wilcoxon rank-sum test.

This analysis will use observed data only.

8.5.10. Change from baseline (28-day run-in) period to Week 12 (previous 28 days, Week 9 through Week 12) in the number of migraines with use of an acute medication

This endpoint will be performed on the mITT analysis set, in addition to the ITT analysis set.

The number of migraines with use of an acute medication will be counted for the run-in period and for post randomization period.

The change from baseline will be calculated as number of migraines in weeks 9-12 minus number of migraines in the run-in period with use of an acute medication.

Migraines that started at one period and ended in the following period will be assigned to the period in which the migraine started.

An Analysis of Covariance (ANCOVA) model will be used to analyse this endpoint. The dependent variable is the change from baseline to Week 12 in the number of migraines with use of an acute medication each participant.

The model will adjust for the following covariates: treatment arm, baseline number of migraines with use of an acute medication. The analysis will use only observed data.

8.5.11. Change in the number of MHDs from baseline (28-day run-in) to Week 12 (previous 28 days, week 9 through Week 12)

This endpoint will be calculated and analyzed as described in Section 8.1.3, using MHDs instead of MMDs.

[figure not shown]
This endpoint will be performed on the mITT analysis set, in addition to the ITT analysis set.

[figure not shown]

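### SAP 8.5.5 and 8.5.10 give no visible rule for an incomplete Weeks 9-12 diary, so a literal count makes stopping the diary look like improvement

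*SAP*

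**What the plan says.** **The two count endpoints.** SAP 8.5.5 scores each recorded headache for severity and states "The change from run-in will be calculated as (Weeks 9-12 number of headaches with at least moderate severity", less the same count in the run-in. It ends "This analysis will use observed data only". SAP 8.5.10 takes "number of migraines in weeks 9-12 minus number of migraines in the run-in period with use of an acute medication" and adds "The analysis will use only observed data". Each is analysed by ANCOVA on arm and the run-in count.

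**Comparable endpoints do have a rule.**
- MMD change (SAP 8.1.1) and MHD change (SAP 8.5.11): missing diary days are imputed, giving 100 complete data sets.
- MSQ (SAP 8.5.6): "In case of missing items, the MSQ score for the visit will be considered missing". MIDAS (SAP 8.5.9) has the same rule.
- Shift in migraine frequency category (SAP 8.8.1): at least 10 reported days in Weeks 9-12, then proration; otherwise missing.

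**How diaries end.** Protocol 4.1.3 makes the diary part of the app: "Participants will continue to utilize the eDiary component in the Study App throughout the study". Under Protocol 7.2 the app on a discontinued participant's "smartphone device will be disabled as described in Section 6.2". For the primary estimand, SAP 2.2 says "data that does not exist after early discontinuation will be considered as missing data, and will be imputed as described in Section 6.3".

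**The concern.** A raw count of recorded events has a value for anyone with part of a window. If the diary stops on day 10 of 28, the remaining 18 days add nothing, and the subtraction turns that silence into a reduction. The run-in is protected, because the protocol synopsis requires at least 80% adherence to the onboarding requirements and Study App before randomization. The visible text sets no such bound for Weeks 9-12, so loss falls mainly on the post-baseline side.

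At stake are two effectiveness estimates from a pivotal trial. Each arm's reported fall would be partly artificial. If more participants stop in one arm, the comparison would favour that arm, whichever it is. The same lost days are imputed for the primary endpoint, so the SAP would be treating one diary in two incompatible ways.

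**Working it through.** **The plan's own figures.** A two-sample t-test with difference 1.6, SD 5.8, 85% power and two-sided 5% gives 236.93, so 237 per arm and 474 in total; 474 / (1 - 0.15) = 557.6, so 558. SAP 4.2 reproduces and is not affected. Its 15% dropout is the only attrition figure in the documents. They give no expected value for either count.

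**Inputs from the documents.** 15% dropout (SAP 4.2), an 84-day intervention, a 28-day window, a 10-day minimum (SAP 8.8.1).

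**Assumptions.** True mean count m of 4, 7 or 10 per 28 days; no true effect unless stated; stopping day uniform within the window, so half the window is lost on average (f = 0.5). A share d of participants stops in the window.

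**1. One participant, 10 of 28 days, unchanged rate.** Raw count = m x 10/28.
- m = 6: 2.14, false change 2.14 - 6 = -3.86.
- m = 4: -2.57; m = 8: -5.14.
- Prorated, m = 6: 2.14 x 28/10 = 6.0, change 0.

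**2. Within-arm fall = m x d x f.** 15% spread evenly over 84 days puts 15% x 28/84 = 5% in Weeks 9-12.
- d = 5%: 0.10 / 0.175 / 0.25 for m = 4 / 7 / 10.
- If the 10% who stopped earlier are excluded for having no Weeks 9-12 data, d = 5/90 = 5.6%: 0.11 / 0.19 / 0.28.

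**3. Equal stopping.** The falls cancel, so the spurious arm difference is 0. A true difference of -1 shrinks to -(1 - 0.05 x 0.5) = -0.975; with 15% stopping in the window, to -0.925.

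**4. Unequal stopping: spurious difference = m x (d1 - d2) x f.**
- 5% vs 10%: 0.10 / 0.175 / 0.25.
- Total dropout of 10% vs 20%, spread evenly, earlier stoppers excluded: d = 3.33/93.33 = 3.57% and 6.67/86.67 = 7.69%, giving 0.08 / 0.14 / 0.21.

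**5. Simulation check.** 1,500 trials per scenario, 237 per arm, ANCOVA on arm and baseline count; person rates gamma with SD 0.43 x mean; 90% same-day entry until stopping; 48-hour back-entry; participants with no Weeks 9-12 entry excluded.
- 5% vs 10%: 0.11 / 0.17 / 0.24. Swapping the arms reverses the sign.
- 15% in both arms: no arm difference; each arm falls falsely by about 0.3 / 0.5 / 0.7.
- For 5% vs 10% the nominal 5% test rejects in 8% / 9% / 12% of trials on raw counts and 5% on prorated counts.
- Isolated missed days alone (85% vs 75% same-day entry): 0.06 / 0.09 / 0.12. Early stopping, rather than scattered gaps, is the main mechanism.

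**The case against.** **The plan never says that unreported days are headache-free.** A reader might infer that it does. It does not: SAP 8.3.2 uses observed data to mean without imputation, and the phrase in 8.5.5 and 8.5.10 could mean that incomplete participants are left out. It also closes the MSQ and MIDAS sections, where incomplete scores are missing. This stands, so the effect is stated only for a literal count. But exclusion would need a completeness threshold, which neither section gives.

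**A rule may sit in withheld text.** A reader might conclude that the plan has none. That cannot be said. Only one paragraph of SAP 6.3 is visible, and 8.8.1 cites that section for proration. The mITT definition and the content of Appendix A are not shown. Against this, other sections cite 6.3 where they rely on it; these two do not. SAP 8 points to Appendix A for migraine qualification and MMD and MHD derivation, without naming these counts.

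**Partial windows may be few.** Protocol 7.2 would ideally observe participants who stop the app to the end of the study, the diary ran alone during the run-in, and Protocol 1.2 (footnote f) triggers a check after 3 days without app activity. SAP 6.3 allows 48-hour back-entry. These reduce the loss. They do not supply a rule for what remains.

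**Little depends on it.** SAP 8.6 makes secondary p-values nominal and bars them from inference. That limits the consequence, but a nominal label does not correct a biased estimate.

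**Conclusion.** The gap is real and should be closed, but it is a second-rank point. In the visible text, both sections subtract recorded counts with no rule for a partial Weeks 9-12 diary. Read literally, stopping looks like improvement.

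If about 5% stop in the window, each arm falls falsely by about 0.1 to 0.3 events, with no arm difference when stopping is equal. An assumed 5% vs 10% gives a spurious difference of about 0.1 to 0.25. These sizes rest on assumed counts of 4 to 10 per 28 days and a uniform stopping day.

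A reader might infer that the plan favours CT-132. The documents do not support that: the 15% dropout is not split by arm, and Protocol 6.1.2 intends similar daily engagement in both. The impact is confined to two secondary endpoints. The primary endpoint and the imputed MMD and MHD endpoints are unaffected.

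**What to change.** In SAP 8.5.5 and 8.5.10:
- Analyse count x 28 / days reported, in both the run-in and Weeks 9-12.
- Set the value to missing below the 10 reported days already used in SAP 8.8.1.
- Define a reported day the same way for headache and headache-free days. SAP 6.3 mentions back-entry of headaches only, whereas Protocol 1.2 (footnote d) speaks of a day's data.
- Keep the ANCOVA, and report days reported by arm and period.
- If SAP 6.3 or Appendix A already applies such a rule to these counts, cite it in both sections instead.

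**Cost.** SAP wording and minor programming; no protocol change. About 10/28 of those who stop in the window become missing: 1.8%, 3.6% or 5.4% of an arm when 5%, 10% or 15% stop. Proration assumes the same event rate on unreported days, so it does not remove bias when people stop because their headaches have changed. For isolated missed days it gains little: with two-day headaches and 85% vs 75% same-day entry, the simulation left an over-correction of 0.04 / 0.07 / 0.10.

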8.1.3. Primary Effectiveness Analysis

An Analysis of Covariance (ANCOVA) model will be used to analyze the primary endpoint. The dependent variable is the change from baseline to Week 12 in MMDs for each participant.

The model will adjust for the following covariates: treatment arm, baseline MMDs, and baseline use of concomitant medications for prevention of migraine. The analysis will be conducted on the ITT analysis set.

Each of the 100 complete datasets will be analyzed using this model. Rubin's rule will be used to combine the results from each of the 100 analyses, resulting in LS mean for the treatments difference and *p*-value associated with the treatment effect. The 95% confidence interval (CI) for the treatment difference will also be constructed. This is considered as the primary analysis for the study, and the study will be considered successful if the p-value is less than 0.05.

LS means for the change from baseline, within each arm as well as the SE, 95% CI and *p-value* for the null hypothesis of no change from baseline versus the two-sided alternative will be presented.

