8.5. Secondary Effectiveness Endpoint and Analysis

Unless otherwise specified, all secondary analyses will be performed on the ITT analysis set.

8.5.1. Proportion of participants who have at least a 50% reduction from baseline (28-day run-in period) in the number of MMDs to Week 12 (previous 28 days, Week 9 through Week 12)

This endpoint will be performed on the mITT analysis set, in addition to the ITT analysis set.

Define R = ((Week 12 (previous 28 days, Week 9 through Week 12) MMDs - Baseline (28-day run-in period) MMDs) / Baseline (28-day run-in period) MMD) *100

For each of the 100 complete datasets, each participant will be indicated as "responder" at week 12 if the reduction is 50% or more (i.e., $R \le 50\%$), and "non-responder" otherwise.

The proportion of patients who have at least a 50% reduction in MMDs will be compared between the two treatment groups using the normal approximation for difference between two proportions, for each of the complete data sets. The results will be combined using Rubin's rule.

8.5.2. Change from baseline (28-day run-in period) in number of MMDs recorded over the previous 28 days at Week 4

The endpoint will be analyzed, using the 100 complete datasets, in the same manner as the primary endpoint.

The week 4 MMDs will be calculated as the number of MMDs in Days 1-28.

8.5.3. Change from baseline (28-day run-in period) in number of MMDs recorded over the previous 28 days at Week 8

The endpoint will be analyzed, using the 100 complete datasets, in the same manner as the primary endpoint.

The week 8 MMDs will be calculated as number of MMDs in the 28 days during Weeks 5-8 (Days 29-56).

8.5.4. Change from baseline (28-day run-in period) in the mean number of MMDs over 12 weeks

This endpoint will be performed on the mITT analysis set, in addition to the ITT analysis set.

The monthly number of MMDs over 12 weeks will be calculated as the average of MMDs over Weeks 1-4, MMDs at Weeks 5-8, and MMDs at Weeks 9-12, to get the average monthly MMDs. The average monthly MMDs will be used in order for the MMDs over 12 weeks to be comparable with the baseline (end of run-in period) MMDs.

The change from baseline will be calculated as the monthly number of MMDs over 12 weeks minus the baseline MMDs.

The endpoint will be analyzed, using the 100 complete datasets, in the same manner as the primary endpoint.

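### Five secondary ANCOVAs (SAP 8.5.5 to 8.5.8 and 8.5.10) leave out the baseline preventive-medication covariate that the primary model uses, and no reason is given

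*SAP*

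**What the plan says.** The SAP sets out the covariates endpoint by endpoint:

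- **Primary, 8.1.3:** the model adjusts for "treatment arm, baseline MMDs, and baseline use of concomitant medications for prevention of migraine".
- **MMDs at Week 4, at Week 8 and averaged over 12 weeks, 8.5.2 to 8.5.4:** "The endpoint will be analyzed, using the 100 complete datasets, in the same manner as the primary endpoint". All the primary covariates carry over. MHDs at Week 12 (8.5.11) are also referred back to 8.1.3.
- **Headaches of at least moderate severity, 8.5.5:** "treatment arm and number of headaches with at least moderate severity at run-in period".
- **MSQ, 8.5.6:** "treatment arm and baseline MSQ". Sections 8.5.7 and 8.5.8 refer back to this model for Weeks 8 and 4.
- **Migraines with acute medication, 8.5.10:** "treatment arm, baseline number of migraines with use of an acute medication".

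The models in 8.5.5 to 8.5.8 and 8.5.10 use observed data only. Protocol 9.4.5 says that these endpoints will be analysed by ANCOVA and leaves the choice of covariates to the SAP, so the two documents do not conflict. SAP 8.6 makes p-values and intervals for secondary endpoints nominal.

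**The concern.** By putting preventive-medication use in the primary model, the sponsor treats it as prognostic for migraine days. It is at least as plausible a predictor of how often acute medication is taken and of how severe headaches are. The variable differs between participants: inclusion criterion 6 admits people on acute treatment alone, and SAP 7.2 tabulates acute-only, first-line and second-line preventive groups at baseline. It is therefore collected and derived already.

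Three things are at stake, none of them large:

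- **Precision.** Any variance that preventive use explains beyond the endpoint's own baseline stays in the error term.
- **Chance imbalance.** The public text (Protocol 6.3, SAP 4.3) describes 1:1 allocation and names no stratification factor. An imbalance in preventive use would be adjusted for in the primary analysis, 8.5.2 to 8.5.4 and 8.5.11, but not in these five models.
- **Missing data.** An observed-data ANCOVA relies on missingness being ignorable given the covariates in the model. With preventive use included, missingness may depend on it.

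**Working it through.** **The plan's own figure.** Inputs from SAP 4.2: difference 1.6, SD 5.8, two-sided alpha 5%, power 85%, dropout 15%.

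- Normal approximation: n per arm = 2 × (1.960 + 1.036)² × (5.8/1.6)² = 2 × 8.978 × 13.141 = 236.0, so 236.
- Exact two-sample t-test: 237 per arm, power 85.01%, total 474, as stated.
- Dropout: 474 / 0.85 = 557.6, so 558, as stated.

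The sample size comes from an unadjusted t-test, so it counts on no covariate gain.

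**What these five models keep.** Each adjusts for the endpoint's own baseline, usually the strongest predictor. If the correlation between baseline and follow-up is ρ, the ANCOVA variance relative to an unadjusted change-score comparison is (1 − ρ²) / [2(1 − ρ)] = (1 + ρ)/2. For an assumed ρ of 0.3 to 0.7 this is 0.65 to 0.85. Most of the available gain is already taken.

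**What the missing covariate could add.** Let R² be the share of residual variance that preventive use explains after arm and the endpoint's own baseline. The documents give no value, so a range is assumed.

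- Fall in SE when the covariate is added = 1 − √(1 − R²)
- Equivalent extra participants = 474 × R² / (1 − R²)

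| Assumed R² | Fall in SE | Extra participants | Power for a design-sized effect |
|---|---|---|---|
| 0 | 0 | 0 | 85.2% |
| 0.01 | 0.5% | 4.8 | 85.5% |
| 0.02 | 1.0% | 9.7 | 85.9% |
| 0.05 | 2.5% | 24.9 | 86.9% |

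The power column uses the normal approximation with 237 per arm and SD 5.8 × √(1 − R²). It applies to an endpoint with the same standardized effect as the primary design. The documents give no effect size for these endpoints.

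**Simulation check.** Assumed: 474 participants, 40% on preventives, residual SD 5.6. Leaving out the covariate raised the SE by 0.3% for a 1-day medication effect and by 1.4% for a 2-day effect. Where preventive use had no effect, including it raised the SE by about 0.1%. By formula, the 1-day effect corresponds to R² = 0.24 / (0.24 + 31.36) = 0.008, just below the range in the table. The 2-day effect gives 0.96 / (0.96 + 31.36) = 0.030.

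**Chance imbalance.** With 40% preventive use (assumed) and 237 per arm, the SD of the difference in proportions is √(0.24 × 2/237) = 0.045. A 1- to 2-day effect then shifts the estimate by about 0.045 to 0.09 days for a one-SD imbalance. The SE is 5.8 × √(2/237) = 0.53 days.

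**The case against.** The strongest reply is that ANCOVA on an endpoint's own baseline is a conventional, prespecified choice, and that randomization keeps the comparison valid with or without stratification. The protocol leaves these covariates to the SAP, so nothing is contradicted. Participants stay on their preventives during run-in, so each baseline may already carry much of the medication's effect. The R² range is an assumption, and the true gain may lie below it. The results are nominal. All of this stands. It limits the point to a small improvement, but it does not explain why four other secondary analyses keep the covariate and these five do not.

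A reader might infer more than the documents support:

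- **That the secondary MMD analyses drop the primary model's covariates.** Sections 8.5.2 to 8.5.4 keep all of them. The headache, MSQ and acute-medication models lack one covariate and keep their own baseline.
- **That the 50% responder comparison (8.5.1) should be replaced by a covariate-adjusted risk difference.** Section 8.5.1 is unadjusted, "using the normal approximation for difference between two proportions", but Protocol 9.4.5 names that method itself, so a change would be a departure from the protocol. It would also carry over to exploratory 8.7.13, and it would need a stated variance estimator before Rubin's rule could be applied. In simulated responder data (279 per arm), the adjusted-to-unadjusted variance ratio was 0.96 to 1.01, which shows no dependable gain.
- **That MIDAS (8.5.9) belongs on the list.** It is analysed by a Wilcoxon test, which the protocol also names. There is no covariate model to extend.

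**Conclusion.** The inconsistency is real and unexplained. The models in SAP 8.5.5 to 8.5.8 and 8.5.10 omit baseline preventive-medication use, while the primary model and the secondary analyses in 8.5.2 to 8.5.4 and 8.5.11 include it. At an assumed partial R² of 1 to 5%, the cost is about 0.5 to 2.5% in standard error, and possibly less. A typical chance imbalance would move an estimate by well under one standard error. The planned comparisons remain valid, and neither the primary result nor any confirmatory claim is affected. This is a minor point, worth making because the remedy is simple and the variable is already in hand.

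**What to change.** Before unblinding, and preferably before database lock (Protocol 9.4 ties SAP finalisation to it), add the baseline preventive-medication term to the ANCOVAs in SAP 8.5.5, 8.5.6 (which carries it to 8.5.7 and 8.5.8) and 8.5.10. Word and code it as in 8.1.3. If the sponsor prefers not to add it, one sentence giving the reason would do.

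The cost is a change of SAP wording and one degree of freedom per model with yes/no coding. No new data are needed. The endpoints, analysis sets and sample size stay as they are, and the protocol needs no change because it left these covariates to the SAP. Leave 8.5.1 alone.

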#### 8.1. Study Assessments

The following effectiveness assessment scales are used in this trial at the times as provided in the SoA (Section 1.2). A description of the scales and the respective scoring algorithms for all endpoints will be provided in the Statistical Analysis Plan (SAP).

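### If MSQ items can be skipped, one unanswered item of 14 voids the visit score, and the observed-data-only MSQ analyses would drop nearly complete questionnaires

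*SAP*

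**What the plan says.** SAP 8.5.6 describes the instrument and its timing: "The MSQ is a 14-item questionnaire that is completed at baseline, Week 4, Week 8, and Week 12". After reverse-coding, the score is "Total score = ([sum of the 14 reversed item scores - 14] / 70) * 100", which needs all 14 items. The missing-item rule follows: "In case of missing items, the MSQ score for the visit will be considered missing". No number of answered items short of 14 is accepted.

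The analysis is an ANCOVA on the change from baseline. Its covariates are stated as follows: "The model will adjust for the following covariates: treatment arm and baseline MSQ". Missing scores are not restored: "This analysis will use observed data only". For Week 8 the SAP says "This endpoint will be analyzed in the same manner as described in Section 8.5.6, using the Week 8 assessment", and 8.5.8 says the same for Week 4. The rule therefore governs three of the listed secondary analyses.

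Four other places bear on the point:

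- Protocol 8.1 and 9.4.5 leave scoring and missing-data handling to the SAP, so this is where the rule has to be set.
- Protocol 8.1.4 says that the MSQ covers three aspects of health-related quality of life.
- SAP 6.2 takes as baseline the latest value at or before the baseline visit, but the schedule in Protocol 1.2 shows no MSQ before that visit.
- SAP 8.6 makes p-values and confidence intervals for secondary endpoints without multiplicity control nominal.

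**The concern.** The rule treats a questionnaire with 13 answers like one that was never opened. Because the endpoint is a change score, both the baseline form and the later form must be complete. A skipped item at Week 4, 8 or 12 removes the participant from that visit's analysis. A skipped item at baseline removes the participant from all three, since there is no earlier MSQ to fall back on. The 100 imputed datasets serve the diary endpoints and do not reach the MSQ.

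The stakes are precision and possibly bias. The secondary analyses are meant for the ITT set, yet this rule could exclude people who did report their quality of life. If skipping is related to disability or differs by arm, the remaining participants may not represent the randomized groups. The SAP is more lenient elsewhere: the migraine-frequency shift analysis in 8.8.1 accepts 10 reporting days in Weeks 9-12 (10/28, about 36%) and prorates. No reason is given for requiring 100% on the MSQ.

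**Working it through.** **The plan's own figure.** The documents give no sample size, effect size or item-missing rate for the MSQ. The only stated size is for the primary endpoint (SAP 4.2): difference 1.6, SD 5.8, two-sided 5%, 85% power. A two-sample t-test gives 236.93, so 237 per arm and 474 in total. Then 474/0.85 = 557.6, so 558 randomized. Both figures reproduce. The 474 is used below only to turn percentages into counts.

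**Inputs for the MSQ rule.** There are 14 items per form and two forms per change score, so 28 items must be answered (SAP 8.5.6). The per-item skip rate q is an assumption, shown as a range.

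**Loss under the rule as written.** With independent skips:

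- share of visit scores lost = 1 - (1 - q)^14
- share of change scores lost, c = 1 - (1 - q)^28
- confidence-interval width relative to no loss = 1/√(1 - c)

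| q (assumed) | visit scores lost | change scores lost | of 474 | CI wider by |
|---|---|---|---|---|
| 0 (answers forced) | 0% | 0% | 0 | 0% |
| 0.1% | 1.4% | 2.8% | 13 | 1.4% |
| 0.5% | 6.8% | 13.1% | 62 | 7.3% |
| 1% | 13.1% | 24.5% | 116 | 15.1% |

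**Direction of the independence assumption.** For a given q, skips that cluster in a few respondents void fewer forms. At the extreme, where the same people skip everything on both forms, the loss falls to q itself, which is 1% rather than 24.5% at q = 1%. Those forms would be empty, so no partial-completion rule would recover them. The table is therefore towards the upper end.

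**What a partial-completion rule would do to the score.** With m the mean of the 14 reversed items, ((14m - 14)/70) × 100 = ((m - 1)/5) × 100. The total is a rescaled item mean. Filling a gap with a mean of answered items stays on the same scale, and a complete form keeps its score because nothing is replaced.

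**What it would recover.** A pooled rule needing any 7 of 14 items fails only when 8 or more are missing; under independence the loss of change scores is below 10⁻⁹ at every rate in the table. The documents do not allocate items to the three aspects, so for a rule by aspect I assume a 4/5/5 split for illustration. Half of an aspect then means at least 2 of 4 or 3 of 5 answered, so each fails with 3 or more missing. At q = 1%:

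- four items: 4(0.01)³(0.99) + (0.01)⁴ = 4.0 × 10⁻⁶
- five items: 10(0.01)³(0.99)² + 5(0.01)⁴(0.99) + (0.01)⁵ = 9.9 × 10⁻⁶
- per visit: 4.0 × 10⁻⁶ + 2 × 9.9 × 10⁻⁶ ≈ 2.4 × 10⁻⁵
- per change score: about 4.7 × 10⁻⁵, or 0.005%, against 24.5% as written

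Respecting the aspects gives up almost nothing in recovery under these assumptions.

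**The case against.** The strongest reply is that this is a prespecified choice and not an error. The rule is complete, programmable and the same in both arms; SAP 8.5.9 treats MIDAS in the same way, and nothing in the documents contradicts it. That stands, and it is why the point is an improvement and not a correction.

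A reader might infer that nearly complete questionnaires will in fact be discarded, or that the SAP expects missing items because it provides for them. The documents support neither. They give no item-missing rate. Protocol 4.1.1 has self-administered scales completed in an app separate from the Study App, without saying whether that app allows an item to be left blank. A clause covering missing items is ordinary contingency wording.

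The remedy also has a fair objection. A pooled threshold of 7 of 14 could score a visit with one aspect wholly unanswered: if each item belongs to one aspect, the smallest of three has at most 4 of the 14 items (14/3 = 4.7). That rules out a pooled threshold, but not a rule set by aspect. Nor does mean substitution cure bias when skipping depends on the content of the skipped item.

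Parts of the SAP are not readable, including most of 6.3 and of 8.7. A supportive MSQ analysis there cannot be excluded, but 8.5.6 states its own rule, so the reading above does not depend on that text.

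**Conclusion.** The point holds conditionally. As written, any unanswered item voids the MSQ visit score, and no imputation restores it in the Week 4, 8 and 12 analyses. Whether this costs anything depends on whether items can be skipped. If they can, the loss is 2.8% to 24.5% of otherwise available change scores for assumed per-item rates of 0.1% to 1% with independent skips, and less if skips cluster. If answers are forced, it is zero.

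The importance is minor. These are secondary analyses with nominal p-values and intervals, and the primary analysis, the success criterion and the sample size are untouched. It would be wrong to read this as a threat to the trial's main conclusion, or as evidence that the MSQ results will be biased; bias is possible only if skipping is related to outcome or arm, on which the documents are silent.

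**What to change.** In SAP 8.5.6, and so in 8.5.7 and 8.5.8, state whether MSQ items are mandatory in the app. Replace the missing-item sentence with a partial-completion rule that respects the three aspects. For example: if at least half of the items in each aspect are answered, each missing item is replaced by the participant's mean of the answered reversed items in that aspect, and the existing total-score formula is applied; otherwise the visit score is missing. List which items belong to which aspect. Keep the all-14-items rule as a sensitivity analysis. The half-of-each-aspect threshold is a proposal; the documents do not dictate one.

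The cost is a sentence or two in the SAP, the item list, a few lines of scoring code and one extra analysis run. It should be settled before database lock and unblinding, so that no scoring decision is left until results are visible. Complete questionnaires keep their scores, and if answers are forced the change does nothing. The downside is small: the rule assumes that skipped items resemble the participant's answered items in the same aspect, so it recovers precision but does not remove bias if skipping depends on the unanswered content.
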